1. **Unconsented data:** SIHHC (hospital discharge projects) taking part in the study (Sites 1-2, 7-13 using clinically led services; Sites 3-4, 14-20 using non-clinically led services) will be asked to provide identifying and demographic data (forename, surname, aliases, date of birth, sex, current or previous postcodes, nationality, ethnicity, NHS number) for service users during the period November 2013 to a maximum of November 2016. However, note that for some services we will collect data that ends before 2016 as some will have been shut down before this time period and in some we may collect data at an earlier point, providing we receive the appropriate permissions and ethical and CAG approvals.
2. **Consented data from a subset of study fieldwork sites (n=6 sites):** We will collect data on 252 individuals across 4 sites with SIHHC (hospital discharge) schemes (two sites that are clinically led (Sites 1&2), two sites that are non-clinically led (Sites 3&4)) and on 126 individuals across two sites with standard /usual care (Sites 5&6), giving 378 individuals in total (63 per site x 6 sites). The data collection for this part of the work is contained in a baseline, exit and 3-month follow up data questionnaire and will collect information on demographic information, along with dates of contact with SIHHC services, past use of health and social care services, mental health services, smoking, alcohol, and drug taking history, prison and homeless history, employment, user satisfaction with service delivery, and data on quality of life (EQ5D). The voluntary sector hospital discharge projects will be asked to help collect this data on behalf of the research team as part of their routine outcomes monitoring and will be reimbursed for doing so at a rate of £20 per completion. The data flow chart shows how this work will be integrated with WP1 for practical purposes.
3. The data flow chart shows how this work will be integrated with WP1 for practical purposes.

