4. **Find and Treat Service Unconsented Data:** In order to compare the outcomes of those individuals accessing SIHHC and standard usual care services to a wider homeless population, we will also use data from Find and Treat NHS clinical service that screens for tuberculosis in homeless hostels in London and people using day centres and the street population accessing soup kitchens and cold weather shelters. To identify hospital admissions during the introduction of SIHHC services (November 2013 to November 2016) we will collect all data from Find and Treat since 2008 as this will allow a period of follow up for this community group to have subsequent hospital admissions.
5. **Personal Demographics Service (PDS):** Where available, NHS number will be collected from the 20 sites. Where it is not available we will use the Personal Demographics Service (PDS) at Health & Social Care Information Centre (HSCIC) to undertake a 'list clean' in order to add an NHS number to as many records as possible.
6. **Linked Hospital Episode Statistics (HES) ONS mortality data:** Once these records have been 'list cleaned' they will then be linked by HSCIC to their linked Hospital Episode Statistics (HES) ONS mortality database to provide data on hospitalisation rates (emergency and planned hospital admissions). In addition to data linked from the 18 SIHHC services and Find and Treat, we will also request a geographically comparable and representative sample of lowest quintile of deprivation population in HES (based upon the index of multiple deprivation) equal in size to the Find and Treat dataset during the hospital admission study period of November 2008 to November 2016 and is therefore likely to be 60,000 records. Unlike the F&T group who are homeless, but not necessarily admitted to hospital, we will collect data on this comparison group to enable us to calculate rates for the primary and secondary outcomes in a group of individuals in the most deprived population that have been admitted to hospital and therefore comparable in terms of history of hospital admission to the homeless individuals at the 20 sites.

Comparative Effectiveness Analysis

Data linkage

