We will provide data from the 20 sites and Find and Treat to the Health & Social Care Information Centre (HSCIC). These records will be list cleaned and then linked by HSCIC to the Hospital Episode Statistics (HES) database to provide data on hospitalisations and A&E attendances and deaths for individuals in the 20 sites and Find and Treat database. In order to be able to identify co-morbidities more accurately we will request data on all previous admissions for these groups for identification of

comorbidities but analyses of admission rates will be confined to the period November 2008 – November 2016.

Study design:

We will construct a virtual cohort that will take first date of admission as the entry point (earliest November 2008) or, for control groups an admission matched by month and year restricted to individuals over the age of 18. Exit from the virtual cohort will be at the end of November 2016 or, if earlier, date of death. We will conduct person-level analyses using Poisson regression to compare overall hospitalisation rates, emergency admission rates, all cause mortality and avoidable mortality rates in:

- 1) Homeless people using the different categories of SIHCC service (clinically led services - sites 1&2, 7-13; non-clinically led services - sites 3&4, 14-20)
- 2) Find and Treat Homeless population and sites 5&6 with standard usual care
- 3) Socially deprived non-homeless population.

We will also conduct analyses at the level of the hospital admission whereby through knowledge of the dates of SIHCC involvement and service user group we will be able to classify hospital admissions in the period November 2008- November 2016) into the following groups:

- 1) Admissions in a socially deprived non homeless population
- 2) Admissions in the general homeless population (Find and Treat data)
- 3) Admissions in homeless service users prior to their first engagement with SIHCC
- 4) Admissions in homeless service users where there is evidence of SIHCC support for that admission
- 5) Admissions in homeless service users that occur following SIHCC support but where there is no record of support for the subsequent admission.

We will use Cox regression survival models and Kaplan Meir plots (accounting for clustering at the level of the hospital and individual) to explore how admissions in these groups compare in terms of the following primary outcomes:

- 1) Time from discharge to next A&E attendance

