Confounding variables: As this is a virtual cohort, we will not be able to collect a complete set of confounding variable data on individuals at entry to the study. Where data is provided by SIHHC services we will include age (year and month only), sex. As a result of the lack of baseline data will use historical HES data to determine past medical history from the age of 18 which will be used to create a variable to control for co-morbid conditions and historical hospital usage. Analyses will therefore control for age, gender, comorbidities (identified from HES data) and reason for admission, classified by Healthcare Resource Group (HRGs – groupings of treatment episodes which are similar in resource use and clinical response). Subgroup analyses will compare the different types of SIHCC services. Where provided by the SIHHC services, we will also control in subgroup analysis for medical symptoms, past use of health and social care services, mental health services, smoking, alcohol, and drug taking history, prison and homeless history, employment history.

Health Economics Analysis:

This analysis will cover three economic models. The primary analysis will be a cost effectiveness model (linked to effectiveness data described in the comparative effectiveness section). This model will take an NHS perspective, with costs based on the linked HES data analysis and outcomes based on morbidity and mortality data. Outcomes of homeless users of the two types of SIHHC service (clinically led and non-clinically led) will be compared to each other and homeless controls. Outcomes used for this analysis will include: 1. Overall hospital readmission rates; 2. Unscheduled readmission rates; 3. 28-day emergency readmission rates. Cost estimates will be calculated using national NHS

tariff data, and will include length of hospital stay, emergency admissions, and fixed and variable costs estimates for each of the SIHHC services.

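### In the admission-level primary analysis, calendar period is not controlled when SIHHC-supported admissions (mostly from November 2013) are compared with groups 1 to 3 (from November 2008)

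*Protocol*

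**What the plan says.** All references are to the protocol.

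- **Study design** (under Comparative Effectiveness Analysis). The admission-level analysis will "classify hospital admissions in the period November 2008- November 2016) into the following groups": (1) a socially deprived non-homeless population, (2) the general homeless population from Find and Treat, (3) service users before first engagement with SIHHC, (4) admissions with evidence of SIHHC support, (5) later admissions without recorded support. Cox models and Kaplan-Meier plots compare the groups on time to A&E attendance, 28-day emergency readmission and time to inpatient readmission.
- **Data sets used for WP2, item 1.** Schemes supply data "for service users during the period November 2013 to a maximum of November 2016", although "in some we may collect data at an earlier point, providing we receive the appropriate permissions and ethical and CAG approvals".
- **Same section, Find and Treat item.** The stated purpose is "To identify hospital admissions during the introduction of SIHHC services (November 2013 to November 2016"), and records are taken back to 2008 so that people have time to accrue later admissions.
- **Same section, linked HES item.** The deprived sample is requested for November 2008 to November 2016.
- **Study design, cohort entry.** Each SIHHC user starts in the virtual cohort at the first admission, no earlier than November 2008. The clause on controls reads "or, for control groups an admission matched by month and year restricted to individuals over the age of 18".
- **Confounding variables.** "Analyses will therefore control for age, gender, comorbidities (identified from HES data) and reason for admission", with HRG codes used for the last of these. Calendar year or period is not named.

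**The concern.** Group 4 can be identified only where a scheme has supplied records, which for most schemes means from November 2013. Groups 1 and 3, and group 2 on the study-design wording, also contain admissions from the five years before that. Group 3 precedes the same person's supported admissions by definition.

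If A&E attendance, emergency readmission, coding or local discharge practice changed nationally over 2008 to 2016, group 4 differs from groups 1 to 3 for that reason alone, and nothing in the stated adjustment removes the difference. The Background section makes such change plausible. It reports a large fall in delayed discharges from 2001 onwards, with the contributing initiatives hard to separate. It gives no trend for the outcomes or years used here.

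All three primary outcomes are affected, in the specialist-versus-no-specialist contrast that Work Package 2 is meant to inform.

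**Working it through.** **Benchmark.** The protocol gives no figure for secular trend, so there is none to reproduce on this point. The nearest yardstick is in Sample size, where a 10% reduction is called important (ratio 0.90). The rates used there, 0.7 and 0.6, give (0.84 + 1.96)² × (0.7 + 0.6) / (0.1)² = 1019 person-years, as stated. They correspond to a ratio of 0.6/0.7 = 0.857.

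**Does the matching cover the five groups?** SIHHC users enter the cohort at their first admission, which may be as early as November 2008, not at the supported admission. Controls matched on month and year to that entry follow the first-admission dates. The matching is not restated for the admission-level groups. For group 3 it could not help, because those admissions belong to the SIHHC users themselves.

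**Calendar gap.** Count years from November 2008 (0) to November 2016 (8). Assume admissions are evenly spread and no scheme supplies data from before November 2013.

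- Group 4 runs from 5 to 8, with mean 6.5.
- Comparators over the full window run from 0 to 8, with mean 4.0. The gap is 2.5 years, and 5/8 = 62.5% fall before November 2013.
- Group 3 runs from 0 to first engagement T, with T uniform on 5 to 8. The mean is E(T²/2)/E(T) = 21.5/6.5 = 3.31. The gap is 3.19 years, and 5/6.5 = 77% fall before November 2013.

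**Spurious ratio with no true SIHHC effect.** For a trend of s per year the ratio is approximately (1 + s) raised to the gap. The trend is an assumption, shown in both directions.

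| Trend per year | v full-window comparators (2.5 y) | v group 3 (3.19 y) |
|---|---|---|
| −1% | 0.975 | 0.968 |
| −2% | 0.951 | 0.938 |
| −4% | 0.903 | 0.878 |
| +1% | 1.025 | 1.032 |
| +2% | 1.051 | 1.065 |
| +4% | 1.103 | 1.133 |

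Averaging the trend over the whole windows, instead of using the mean gap, gives nearly the same values (for −2%: 0.950 and 0.937). A spurious ratio of 0.90 then needs about −4.0% a year against full-window comparators, or −3.2% against group 3. A ratio of 0.857 needs about −5.7% or −4.6%.

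**Season.** Three whole years against eight whole years give a seasonal ratio of 1.000, even with a 20% seasonal amplitude.

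**The case against.** Several arguments on the other side have force.

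- **Calendar time is not ignored.** Controls are matched on month and year, and the admission-level analysis follows under the same heading. A reader might infer that the plan overlooks calendar time altogether, and the text does not support that. But the matching is tied to cohort entry, is not said to extend to the supported admission, and cannot reach group 3.
- **Supported admissions before November 2013 are possible.** Some services may supply earlier data, so it would be wrong to say that supported admissions occur only from that date. The gaps above shrink to the extent that they do.
- **Find and Treat may be contemporaneous.** The data-sets section ties its purpose to admissions in November 2013 to November 2016. On that reading the gap for group 2 is about zero. Even on the wider window, if admissions rise linearly as screened people accumulate (an assumption), 25/64 = 39% precede November 2013, the gap is 6.5 − 5.33 = 1.17 years, and a 4% trend gives about 1.05. The two sections still need reconciling.
- **A seasonal bias might also be inferred.** The planned windows are whole years, so this is unsupported unless schemes close part-way through a year.
- **Calendar strata could sit in an analysis plan that is not shown.** That is possible. But the protocol states a control list for its analyses, and calendar period is not among the variables named, although Sample size allows for about ten confounders.

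**Conclusion.** The point holds for comparisons of group 4 with groups 1 and 3, and with group 2 on the study-design wording. As written, the primary admission-level analysis does not separate calendar period from SIHHC support.

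The result is a risk of bias of unknown size and direction. Under even spread and a trend of 1 to 4% a year, the spurious ratio is about 0.90 to 0.98 or 1.03 to 1.10, reaching about 0.88 or 1.13 for group 3. Only the upper end of that assumed range matches the 10% the protocol calls important.

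A reader might go further and conclude that Objective 3 as a whole cannot be separated from time trend. The documents do not support that. Group 5 follows SIHHC support and so overlaps group 4 in time. The contrast between clinically led and non-clinically led services, on which the sample size rests, is also largely contemporaneous.

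**What to change.** 1. In every comparison involving groups 1 to 3, stratify the Cox models by calendar period of the index admission (year or quarter), or adjust for it. Add calendar period to the list under Confounding variables.
2. State whether month-and-year matching applies to the supported admission or only to cohort entry.
3. Reconcile the Find and Treat admission window in the data-sets section (from November 2013) with the study-design window (from November 2008).
4. Report, as a sensitivity analysis, groups 1, 2, 4 and 5 restricted to November 2013 to November 2016. This should not be the main analysis: it leaves out group 3, where the gap is largest, and under even spread discards up to 62.5% of comparator admissions.

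The cost is a change of wording, since admission date is already among the HES variables requested in Appendix One, Box 5. The downside is precision for group 3 versus group 4. That contrast would rest mainly on periods where their dates overlap, and under the assumptions above only about 23% (1.5/6.5) of group 3 admissions fall after November 2013.

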Where formal protocols (without specialist provision) seemed to have driven improvements, a number of factors appear relevant. These include effective joint working at both operational and strategic levels, good communication between agencies, the provision of training (especially induction) and considerable efforts to keep protocols 'live' (e.g. regular meetings, phone calls and personal contacts between partners) (Homeless Link 2012 p10). In a number of areas visited by Homeless Link, 'specialist provision' appeared to have evolved from protocols that had started out as cross-agency referral agreements. In York, for example, hospital staff would refer homeless service users to the Salvation Army who would then provide support and advocacy, such as organising the housing support related side of the discharge including ensuring that hostel staff were briefed on the person's health needs. This bridging role led the Salvation Army to develop a visible presence in the hospital ('in-reach') and to provide training to hospital staff on the needs of homeless people (reported in Homeless Link, 2012 p8).

In London and inner city areas with higher populations of homeless people a number of specialist schemes have been developed which are GP or nurse (clinically) led. A number of different models fall within this typology. For example, in the Royal Liverpool University Hospital (RLUH) a nurse-led team is responsible for the discharge of service users who are homeless. The team comprises a 'link nurse', a substance misuse nurse, an adult safeguarding lead, and three hospital outreach workers providing 27/4 housing and welfare benefits support to homeless people. The RLUH team then link homeless people into the vulnerable persons' team at a specialist primary care centre (Brownlow) which includes access to a GP, two homelessness nurses, an alcohol outreach nurse and a Hepatitis C nurse.

Another high profile (award winning) 'clinically led' model is the Pathway approach. This approach was pioneered at University College Hospitals London (UCH) and has since been adopted across a further three London hospital sites as well as in Bradford, Leeds, Manchester and Brighton. The

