Unique Study ID created for
 Each individual record and left
 On site

Box 5: Data variables collected for WP2:**Linked HES / ONS data variables requested**

Field name (where known)	Description of contents
admidate	Date of admission
elecdate	Date of decision to admit
admimeth	Method of admission
admisorc	Source of admission
firstreg	First regular day or night admission
elecdu	Waiting time
disdate	Date of discharge
disdest	Destination on discharge
dismeth	Method of discharge
DISREADYDATE	Discharge ready date (delay in discharge)
ARRIVALDATE	Arrival date
AEATTENDCAT	Attendance category
AEATTENDDISP	Attendance disposal
TREAT2_N	treatment
APPTDATE	Appointment date
ATTENDED	Attended or did not attend
TRETSPEF	Treatment specialty
cause_of_death	Original underlying cause of death
cause_of_death_non-neonatal	Non-neonatal cause of death mentions
	Match rank (ranking of quality of match)
dod	Date of death

SIHHC data variables

Other than the demographic information, we expect few sites to contain all the data variables listed below, but where they are (and for example we know of several sites that collect EQ5D data on all service users) we will collect these unconsented data. The list below therefore provides a potential list of variables we would attempt to collect at each site.

Example field name (where known)	Description of contents
date_interviewed	Date of interview
first_name	First name
surname	Surname
middle_names	Middle names (s)
Alias	Any alias names
sex	Sex of individual
address1	Address line 1
address2	Address line 2
address 3	Address line 3
postcode	postcode

telephone	Home telephone number
mobile	Mobile telephone number
plbirth	Place of birth
ethnicity	Ethnicity
Date_admission	Date of hospital admission
Ad_diagnosis	Admitting diagnosis
Date_discharge	Date of hospital discharge
sympwloss	Currently has symptoms of weight loss for no reason
sympcough3w	Currently has been coughing for more than 3 weeks
sympfevns	Currently has fever or night sweats
symphaemopt	Currently is coughing up blood
sympsob	Currently has shortness of breath
symprone	Currently has none of these symptoms
gpyeslocal	Registered with Local GP
gpnotlocal	Registered with GP that is not local
noreggp	Not Registered to GP
ae_visits	Number of A&E visits in the last year
op_visits	Number of hospital outpatient user visits in the last year
hospitalisations	Number of hospitalizations in the last year
vaxhepb	Individual been vaccinated against Hepatitis B

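### Admissions from 2008 to 2016 are grouped by SIHHC support, but support records are secured only from November 2013 and only at 18 services, so some supported admissions will sit in groups 2, 3 and 5

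*Protocol*

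**What the plan says.** Under Comparative Effectiveness Analysis, Study design, the protocol will "classify hospital admissions in the period November 2008- November 2016) into the following groups", and will do so "through knowledge of the dates of SIHCC involvement and service user group". The five groups are:

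1. a deprived non-homeless population;
2. the general homeless population from Find and Treat;
3. "Admissions in homeless service users prior to their first engagement with SIHCC";
4. admissions with evidence of SIHHC support;
5. later admissions by previously supported people where no support is recorded.

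All three primary outcomes (time to next A&E attendance, 28-day emergency readmission, time to next inpatient readmission) are compared across these groups.

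The support records come from the unconsented extract (Data sets used for WP2, item 1). Sites 1-4 and 7-20, which are 18 services, supply data "for service users during the period November 2013 to a maximum of November 2016". The same item says that "some will have been shut down before this time period and in some we may collect data at an earlier point", the latter subject to permissions and approvals. That item asks for identifying and demographic data. Dates of interview, admission and discharge appear in Appendix One, Box 5, as part of a potential list, with the caveat "Other than the demographic information, we expect few sites to contain all the data variables listed below".

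**The concern.** An admission can be placed in groups 3 to 5 correctly only if it is known whether a scheme supported it. The classification covers eight years, while the secured records cover at most the last three, and only from participating services. The study design does not limit groups 2 to 5 to hospitals and periods with records, and has no category for unknown support. In practice, a missing record is handled as missing support.

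What is at stake is the exposure variable of every primary admission-level comparison. If support lowers readmission, supported admissions inside the comparison groups make those groups look better and shrink the estimated effect. Support dates that were never requested cannot be recovered at the analysis stage.

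**Working it through.** **Step 1: the windows.**
- Classification: November 2008 to November 2016, 96 months (Study design).
- Secured scheme records: November 2013 to November 2016 at most, 36 months (Data sets used for WP2, item 1). Earlier records are possible at some services and later ones are cut short at others.
- Services supplying records: sites 1-4 and 7-20, so 4 + 14 = 18.

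**Step 2: was there support outside those records?** The Background section says so in four ways.
- On Pathway: "This approach was pioneered at University College Hospitals London (UCH) and has since been adopted across a further three London hospital sites", and other cities besides. A source dated 2012 is cited for the first full year of the UCH service, so that service ran well before November 2013.
- A link worker scheme in Wirral had an evaluation dated 2011.
- The 2013 Department of Health fund supported 52 schemes, against 18 participating services.
- Some inner-city areas have a nest of several schemes, and Site Selection deliberately seeks such nesting for Sites 1 and 2. A patient in a participating hospital may thus be helped by a scheme that supplies no records.

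**Step 3: the routes into the wrong group.**
- Group 3: a person supported before records begin, or by a non-participating scheme, and first recorded later. The earlier supported admission counts as before first engagement.
- Group 5: a recorded person readmitted with help from a scheme that supplies no records. The label is accurate, but the group mixes supported and unsupported admissions.
- Group 2: Find and Treat is a London service, and London had several Pathway sites. Its members may have been supported without a record.
- Overlap: no rule covers a person on both the Find and Treat list and a scheme list, so one admission can meet groups 2 and 4.

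**Step 4: illustration of the effect on the contrast.** The plan's own figure comes first (Sample size):

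(0.84 + 1.96)² × (0.7 + 0.6) / (0.7 − 0.6)² = 7.84 × 1.3 / 0.01 = 1019 person-years per group, doubled to 2038 for confounders. It reproduces.

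Let m be the share of the comparator that was in fact supported. The comparator rate becomes 0.7(1 − m) + 0.6m = 0.7 − 0.1m. The requirement comes from the same formula. Power at 1019 person-years is Φ(d / √((comparator rate + 0.6)/1019) − 1.96), where d is the rate difference. The documents give no value for m; those below are assumptions.

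| m (assumed) | Comparator rate | Difference | Rate ratio | Person-years needed | Power at 1019 |
|---|---|---|---|---|---|
| 0 | 0.700 | 0.100 | 0.857 | 1019 | 80% |
| 5% | 0.695 | 0.095 | 0.863 | 1125 | 76% |
| 10% | 0.690 | 0.090 | 0.870 | 1249 | 72% |
| 20% | 0.680 | 0.080 | 0.882 | 1568 | 62% |
| 40% | 0.660 | 0.060 | 0.909 | 2744 | 40% |

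The formula is for person-level rates, so the table is only indicative for the admission-level Cox models.

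**The case against.** The strongest reply is that most of the months without records are not missing anything. Many link worker schemes were created with the 2013 fund, and the Find and Treat item dates the introduction of SIHHC services to November 2013. Before a scheme opens, or after it closes, it supports nobody. This stands. A reader might infer from the windows that 60 of 96 months (62.5%) lack exposure data, or 72 of 96 (75%) for a scheme that closed in November 2015. The documents do not support either figure as a share of missing support.

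Other points stand in part:
- 18 against 52 does not measure missed support, because schemes overlap geographically. Misclassification in group 5 needs the same person to be helped by a different scheme.
- The evidence of support before November 2013 is specific only for the UCH service and Wirral. No text fixes UCH as a participating site.
- Box 5 does list interview, admission and discharge dates, and its caveat says that few sites hold every variable, not that dates will be absent. But the list is described as potential, so the dates are not secured.
- A rule for overlapping groups is ordinary content for an analysis plan. The choice of extract fields and coverage dates is not, because it must be settled before data are requested.

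A reader might also infer that the dilution is stronger for clinically led services because Pathway is longer established. This is not shown. Wirral was an early link worker scheme, and a direct comparison of the two service types need not use groups 2, 3 or 5.

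**Conclusion.** The point holds. The protocol classes eight years of admissions by support dates that it secures only for the last three, and only at 18 services. Its own background shows specialist support outside those records. Some supported admissions will be placed in groups 2, 3 and 5, and nothing assigns a person on both lists to a single group.

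The direction is towards no difference in the primary admission-level contrasts, on two assumptions: that support lowers readmission, and that the misplaced admissions otherwise resemble those they are grouped with. The size cannot be derived from the documents. At the planning rates, each 10 percentage points of misclassified comparator removes 10% of the rate difference. That is a scale for judging the problem, not an estimate of it.

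**What to change.** 1. For each participating scheme, obtain its operating start and end dates and the dates its records cover. Make the date of each supported admission, or of scheme contact, a required field in the unconsented extract. Leave sites that cannot supply it out of the admission-level analysis.
2. Keep admissions at a participating hospital before its scheme opened or after it closed as unsupported, unless another specialist team is known to have worked there. Set admissions made while a scheme operated but outside its record dates to support unknown, and exclude them from the main contrast. Excluding everything outside the record dates would discard valid pre-launch comparators.
3. Move anyone on both the Find and Treat and scheme lists out of group 2 and into groups 3 to 5.
4. Add a sensitivity analysis that drops group 2, 3 and 5 admissions at hospitals known to have had a homeless discharge team at that date without supplied records.

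The cost is protocol wording, a few extract fields and analysis code, with fewer admissions in the main analysis. Item 1 has to be settled before approvals are sought and data are extracted.
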